3.4. Test Hypothesis and *P* Value Justification

The study has a planned interim analysis to review the effect size assumption used to determine the sample size. To control for the overall alpha for the primary efficacy analysis, an alpha of 0.0001 will be used for the interim analysis, and alpha of 0.0499 will be used for the final analysis. The details of the interim analysis, including scope, method, and decision rules, will be described in the Data Monitoring Committee charter.

In the final analysis, there are two null hypotheses for the primary efficacy endpoint conspicuity.

1. there is no difference between the IC high dose and the normal saline

2. there is no difference between the IC low dose and the normal saline

Multiplicity due to the two null hypotheses will be controlled by Hochberg method. That is, to control family-wide Type I error to be less than or equal to 0.0499, the two p-values will be ordered from large to small. When both nominal p-values are less or equal to 0.0499, both null hypotheses will be rejected and one will conclude that both IC dose groups are statistically different from the saline group in the examined parameter. When the larger nominal p-value is greater than 0.0499 but the smaller p-value is less or equal to 0.025, the null hypothesis associated with the larger p-value is accepted and the null hypothesis associated with the smaller nominal p-value will be rejected. If the smaller nominal p-value is greater 0.025, the null hypothesis associated with this p-value is also accepted. The Overall Type I error control will apply to the primary endpoint conspicuity only.

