where $Z = (\hat{T} / \text{SE})$

3. 100(1- γ) confidence interval for conditional power on the basis of \hat{T} and SE

$$\text{ProbNorm} \left\{ \sqrt{\frac{(1-P)}{P}} \times (Z \pm Z_\gamma) + \sqrt{\frac{P}{(1-P)}} \times Z - \frac{Z_\alpha}{\sqrt{1-P}} \right\}$$

Where T_{hat} = estimate of treatment effect at interim and SE = standard error of the treatment effect. In this study, T_{hat} will be the estimate of odds ratio of treatment and SE will be the standard error of the estimate, both are in the log scale. P =proportion of study completed (=0.5), alpha (α)=0.05/2, gamma (γ)=0.05

Following Mehta et al (2011, page 6)² adaptive approach the interim analysis results will be classified into three zones based on the estimated CP and decision to be made in each zone is specified as follows.

¹ Page 8 “Statistical Considerations for the Conduct and Reporting of Interim Analyses”. (GGK 8/11/2003)

² Adaptive increase in sample size when interim results are promising: A practical guide with examples. Cyrus R. Mehta and Stuart J. Pocock. Statist. Med. 2011, 30 3267--3284

Table 3: Interim Analysis Conditional Power and Decision Principle

Conditional Power	Decision	Rationale
CP <0.20	Stop the study because the evidence for unfavorable efficacy is sufficiently convincing that no additional efficacy data is necessary.	An unfavorable zone: the conditional power (CP) is fairly low, suggesting that the final result is not likely to achieve significance, hence, the study has fairly low probability to reject the null hypothesis. This zone is defined to be CP < 40%
0.2 <=CP <0.4	No sample size re-estimate because the evidence for unfavorable efficacy. Complete the study per current protocol.	
0.4 <=CP <=0.8	Re-estimate sample size, study continues to complete the enrollment per re-estimated sample size	A Promising zone: the conditional power is in between 40% to 80%, suggesting that the interim analysis result is promising, but the study has to have an increased sample size to have at least 80% power to reject the null hypothesis
CP > 0.8	No sample size re-estimate. Complete the study per current protocol.	A favorable zone: the conditional power is fairly high, suggesting that the interim result is as good or better than the expectation, the study has fairly high probability to reject the null hypothesis as is. This zone is defined to be CP > 80%.

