response. The model estimates the cumulative logits of better outcome (conspicuity=5) to the poor outcome (conspicuity=1). Since it is expected that the interaction effect will not be statistically significant ($p > 0.10$), a reduced model (**Model 2**) will also be used in which the interaction effect will be dropped. The goodness of fit of the models (Full model vs the Reduced model) will be evaluated. A REPEATED statement will be used to control for the repeated measures within a subject. The difference between the IC high dose vs saline, the IC low dose vs saline will be presented in the summary along with the estimates and 95% confidence intervals of the estimates. Effect of a source (treatment, ureter, treatment*ureter interaction in full model) will be determined based on the Score Statistics for Type 3 GEE Analysis.

For the primary endpoint analysis, GEE models will be fitted separately for each comparison, namely IC High dose vs Saline, and IC Low dose vs Saline, and IC High dose vs IC Low dose.

An example of SAS syntax is showing below for this analysis, in which the conspicuity is treated as an ordinal response variable and a proportional odds model is used model the better response compared to the poorer response. Stokes et al. (2000)³ recommended that the null hypothesis of treatment effect would be based on the score statistics for Type 3 GEE analysis, whereas the parameter will be the GEE parameter estimates with the empirical standard error because the Z and the Wald statistic generally produce more liberal p-value than the score statistic.

In this example, the treatment is a binary code; IC High dose=1 and Saline=0. For analysis of IC Low dose vs Saline, IC Low dose=1 and Saline=0; when comparing IC High dose vs IC Low dose, IC High dose=1 and IC Low dose=0.

```

PROC GENMOD DATA=respH descending;
  CLASS USUBJID URETER(ref='Right') TRT (ref='Saline');
  MODEL conspicuity = trt ureter trt*ureter
    /LINK=clogit DIST=mult TYPE3; (Model 1)
  REPEATED subject = Usbjid / type=ind;
  ESTIMATE 'OR: IC vs Saline' trt 1 -1/ exp;
  ods output Estimates=OR1 GEEEmpPEst=est1 Type3=pval1;
  Run;

PROC GENMOD DATA=respH descending;
  CLASS USUBJID URETER(ref='Right') TRT (ref='Saline');
  MODEL conspicuity = trt ureter
    /Link=clogit DIST=mult TYPE3; (Model 2)
  REPEATED SUBJECT = Usbjid / type=ind;
  ESTIMATE 'OR: IC vs Saline' trt 1 -1/ exp;
  ods output Estimates=OR2 GEEEmpPEst=est2 Type3=pval2;
  Run;

```

Where:

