³ Stokes ME, David CS, Koch GG (2000). Categorical Data Analysis using the SAS System 2nd Edition (page 485).

1. Dataset respH include subjects from IC High dose only.
2. The ‘descending’ option indicates that the ordered values are listed in descending order.
3. Conspicuity score (1, 2, 3, 4, or 5)
4. ‘TRT’ is Treatment (coded to IC or Saline)
5. ‘URETER’ is coded to ‘Left’ or ‘Right’
6. ‘USUBJID’ is the unique Subject Identification
7. REPEATED statement controls the intra-subject correlation due to repeated measures. In this example, independent correlation matrix is used.
8. Three output datasets:
 - a. OR=estimated odds ratio (IC /Saline)
 - b. EST= Analysis of GEE Parameter Estimates based on Empirical Standard Error Estimates
 - c. PVAL= P-value for each effect in the model per Score Statistics For Type 3 GEE Analysis

The analysis summary table (**Table 14.2.1.1**) will include distribution of conspicuity score in each treatment group by ureter (left vs right and overall), p-value based on score statistics for Type 3 GEE analysis, odds ratio estimates and standard error, and 95% confidence intervals for the odds ratio. Three treatment group comparisons will be provided, namely difference between IC High dose vs Saline, IC Low dose vs Saline and IC High dose vs IC Low dose (an exploratory analysis).

The summary table will display the nominal p-values from each comparison (High dose vs Saline, Low dose vs Saline, and High dose vs Low dose). However, the statistical significance of the normal nominal p-value between the IC High dose vs Saline and between the IC Low dose vs Saline will follow the rule defined in [Section 3.4](#) in order to control for family-wide type I error for the primary endpoint.

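### Minor: SAP section 3.4 sets Hochberg's second step at 0.025, but half of the stated final level of 0.0499 is 0.02495

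*SAP*

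**What the plan says.** SAP section 3.4 divides the alpha between the two looks: "an alpha of 0.0001 will be used for the interim analysis, and alpha of 0.0499 will be used for the final analysis". It then names two null hypotheses for conspicuity, one per IC dose against saline, and applies Hochberg's method "to control family-wide Type I error to be less than or equal to 0.0499".

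The rule has two steps. If both p-values are at or below 0.0499, both nulls are rejected. Otherwise the smaller p-value is compared with 0.025. That limit is printed twice, once for rejection ("When the larger nominal p-value is greater than 0.0499 but the smaller p-value is less or equal to 0.025") and once for acceptance ("If the smaller nominal p-value is greater 0.025, the null hypothesis associated with this p-value is also accepted").

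SAP section 5.1 gives no threshold of its own. It refers significance of the two dose-versus-saline comparisons back to section 3.4, "in order to control for family-wide type I error for the primary endpoint".

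**The concern.** With two hypotheses, Hochberg's critical values are alpha for the larger p-value and alpha/2 for the smaller. Section 3.4 takes alpha as 0.0499 in the first step and, in effect, as 0.05 in the second, so the rule does not match the family-wise level stated in the same paragraph.

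This is the plan's only confirmatory decision rule, because section 3.4 limits Type I error control to the primary endpoint. A programmer who runs a standard Hochberg routine at 0.0499 would apply 0.02495; one who follows the text would apply 0.025. If a p-value fell in the gap, the choice between them would be made after the data were seen.

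**Working it through.** **Inputs from the SAP**

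- Interim alpha 0.0001; final alpha 0.0499; two hypotheses; Hochberg; printed limits 0.0499 and 0.025 (section 3.4).
- Dependence between the tests: the documents give no correlation. Section 5.1 says "GEE models will be fitted separately for each comparison" and, for its example, "Dataset respH include subjects from IC High dose only". Each dose is then compared with its own subjects' saline scores, so approximate independence is inferred.

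**Assumptions:** uniform p-values; the futility stop and sample size re-estimation in section 3.2 are ignored.

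**1. The plan's own figures.** The split reproduces: 0.0001 + 0.0499 = 0.0500. The second step does not: 0.0499/2 = 0.02495. The printed 0.025 comes out only as 0.05/2, and is too high by 0.00005.

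**2. Family-wise error, both nulls true, independent tests.** With a = 0.0499 for the larger p-value and c for the smaller, FWER = a² + 2c(1 − a).

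- c = 0.025: 0.00249001 + 2 × 0.025 × 0.9501 = 0.00249001 + 0.04750500 = 0.04999501.
- c = 0.02495: 0.00249001 + 2 × 0.02495 × 0.9501 = 0.04990000.

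As written, the error exceeds 0.0499 by 0.000095. With 0.02495 it equals 0.0499.

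**3. Correlated tests** (bivariate normal, two-sided, both nulls true, limits as written)

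| Correlation | FWER |
|---|---|
| 0 | 0.049995 |
| 0.05 | 0.049977 |
| 0.10 | 0.049925 |
| 0.116 | 0.049900 |
| 0.15 | 0.049836 |
| 0.25 | 0.049544 |
| 0.50 | 0.048009 |

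The excess is gone above a correlation of about 0.116.

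**4. Only one null true.** The true null can be rejected only if its own p-value is at or below 0.0499, so that bound holds. For independent tests the error is 0.025 + (0.0499 − 0.025) × power of the other test. At an assumed power of 0.80 this is 0.025 + 0.0249 × 0.80 = 0.04492.

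**5. Adding the interim alpha as a simple sum.** 0.0001 + 0.049995 = 0.050095 as written; 0.0001 + 0.0499 = 0.0500 after the correction. The sum is an upper bound; see the objection.

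**6. How often the two limits give different conclusions.** The smaller p-value must lie in (0.02495, 0.025] and the larger must exceed 0.0499.

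- Both nulls true, independent: 2 × 0.00005 × 0.9501 = 0.000095.
- Independent normal tests, each dose at an assumed power of 80%: 0.000105; at 90%: 0.000037.
- Largest value over assumed powers of 5% to 99% for each dose: about 0.00032, near 37% power for both.

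**The case against.** **Rounding.** To three decimals, 0.02495 is 0.025. Section 3.2 is equally loose: it computes conditional power at the two-sided 0.05 level, not at 0.0499. But that figure is a planning input, whereas 0.025 is a decision limit printed beside a four-decimal 0.0499 and rounded in the anti-conservative direction. The rounding costs up to 0.000095, almost the whole 0.0001 set aside for the interim. Rounding may explain the figure but does not make the rule correct.

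**The total of 0.050095 carries little weight.** This stands.

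- Table 3 in section 3.2 has no stop for efficacy. Even in the favorable zone the decision is "No sample size re-estimate. Complete the study per current protocol", so the interim alpha may never be spent on a rejection.
- The interim model pools the doses against saline and so tests neither dose-specific null.
- If the 0.0001 were spent, a simple sum ignores the overlap between the looks. A simulation with a pooled interim at 50% information, independent dose tests and both nulls true gives about 0.05002 as written and 0.04993 with 0.02495.

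**The planned test is asymptotic.** Its approximation error may be far larger than 0.000095. Take the score statistic as (Σd)²/Σd² on normal within-subject contrasts d, with an assumed 47 subjects per dose (about half of the 95 in section 3.2). Nominal 0.025 then has an actual size of about 0.0233, and nominal 0.0499 about 0.0488. The rule as written gives a family-wise error of about 0.0467, with a range of 0.0461 to 0.0474 for 40 to 58 subjects per dose. This is only an approximation for ordinal data, but it means that a breach of 0.0499 in practice is not shown. The excess is one of nominal levels.

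**Independence is inferred.** Sections 3.7 and 5.1 also describe one pooled saline group, about twice the size of each dose group. A shared comparator could correlate the tests and remove the excess. This stands as a limit on the size of the effect.

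None of these points changes the arithmetic: at 0.0499, the second Hochberg step is 0.02495.

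**Conclusion.** The concern holds as a minor error in the written rule. The two steps in section 3.4 use different alphas, and nothing else in the documents reconciles them.

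The stated 0.0499 is exceeded, by at most 0.000095 on the cases computed, only when both nulls are true and the two tests are close to independent. The final-analysis error stays below 0.05 under the stated assumptions. The result does not rest on the interim alpha being spent, and it does not show that Type I error is inflated in practice. The reason to act is that a prespecified primary decision limit should agree with the level it claims to control.

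**What to change.** In SAP section 3.4, replace 0.025 by 0.02495 in both the rejection and the acceptance sentence. Section 5.1 then needs no edit, because it refers to that rule. Section 3.2 can stay as it is. The cost is one number in two sentences, with no effect on data collection, sample size or the interim analysis.

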3.5. Procedures for Handling Missing Data

Missing or partial data associated with efficacy assessments will be discussed specifically within each section. No missing data imputation will be performed for safety parameters. However, AEs with missing severity assessments will be tabulated as “severe,” and AEs with missing relationship assessments will be tabulated as “related” for the purpose of analysis; and the missing data will be presented in data listing as is.

3.6. Analysis Center

This is a multicenter study; however investigative center will not be included in the analysis model as a covariate due to expected small sample size per center, additionally, the primary efficacy conspicuity score data will come from central readers whereas the conspicuity score from the local readers (surgeons) will be used for confirmatory analysis. Potential center effect will be assessed if data suggested.

3.7. Treatment Group vs Randomization Group

All qualified subjects will be randomized to either a dose of 2.5 mL IC (referred to as the Low dose) or a dose of 5.0 mL IC (referred to as the High dose). All randomized subjects will receive a dose of normal saline before receiving the randomized IC dose.

Hence, there are 2 randomization groups, namely IC High Dose and IC Low Dose and 3 treatment groups (IC High dose, IC Low dose, and Saline) in this study.

If a dosing error occurred (e.g., a subject was randomized to the IC High dose but actually received IC Low dose, and vice versa), the subject will be included in the actual treatment group received for efficacy, PK, and safety analyses; this will be an important protocol deviation and the incident will be clearly documented in the study report and in the database.

Data presentation for study population, physician overall satisfaction, safety lab, and 12-ECG will be based on the 2 randomization groups; whereas the data presentation for conspicuity, TTV, adverse events, and vital signs will be based on the 3 treatment groups. A Study Overall group may be included in certain data presentations (e.g., demographics) if data warrant. The Saline group will include all subjects who had saline dose, hence, the number of subjects in this treatment group will expect to be twice the size of IC Low dose and IC High dose. If data warrants, the Saline group may also be split by IC dose group. That is, subjects received the IC Low dose vs subjects received the IC High dose.

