3.3. Analysis Population

The following analysis sets will be identified for this study.

Enrolled Analysis Set: All subjects who sign the ICF for the study are considered to have enrolled.

Intent-to-Treat (ITT) Analysis Set: The ITT Analysis Set will include all randomized subjects. This dataset may also be referenced as the 'Randomized Set'. The ITT subjects may or may not receive randomized treatment. All ITT subjects will be included in the randomized treatment group even if a dosing error occurred. See additional discussion in [Section 3.7](#).

Safety Analysis Set: The safety set will include all ITT Analysis Set subjects who are treated with any study drug (Saline or IC) and will be used for safety and tolerability assessments. In the safety analysis set all subjects will be included in the actual treatment group received if a dosing error occurred. See additional discussion in [Section 3.7](#).

Efficacy Analysis Set: The efficacy analysis set includes all Safety Analysis Set subjects who have a surgical procedure to assess ureteral patency and who have received both study drugs (Saline and IC dose) and a video approximately 10 minutes in length is available after each treatment. **The 21 patients who were randomized and treated prior to the development of the conspicuity score will be excluded from the efficacy population.** This will be the primary population for efficacy assessments. This is also referenced as the modified intent-to-treat (mITT) Analysis Set. All efficacy evaluations will be based on the mITT population. In the mITT analysis set all subjects will be included in the actual treatment group received if a dosing error occurred. See additional discussion in [Section 3.7](#).

Per Protocol (PP) Analysis Set: The PP set includes all subjects from the Efficacy Analysis Set who did not have any major protocol deviation that may confound the interpretation of the efficacy assessment. This Analysis Set will serve as a confirmation analysis set for efficacy analysis. In the PP analysis set all subjects will be included in the actual treatment group received if a dosing error occurred. See additional discussion in [Section 3.7](#).

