4.1. Disposition

A summary table (**Table 14.1.1.1**) will provide frequency counts for subject disposition, including all enrolled subjects, randomized subjects, treated subjects (Saline or IC), subjects who completed study, subjects who did not complete study, and reason for not receiving Saline injection or IC injection, and reasons for study discontinuation.

Primary reason for early termination of study will include

- 1) Adverse Event
- 2) Study Non-compliance
- 3) Lost to Follow-Up
- 4) Physician Decision
- 5) Sponsor Decision
- 6) Subject Decision
- 7) Other

If a subject who receives a dose of normal saline injection and fails to receive a dose of IC, the subject will be considered to have discontinued study drug treatment. Reason for treatment discontinuation will be captured and tabulated. Moreover, the disposition table will identify number (%) subjects included for safety analysis set, efficacy analysis set (mITT), and efficacy per protocol (PP) analysis set.

Another summary table (**Table 14.1.1.2**) will be produced to provide number of subjects in the safety, mITT, and efficacy PP analysis set by investigator and will display the center with the highest enrollment first.

Disposition summary will be based on the ITT analysis set.

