7. SAFETY AND TOLERABILITY EVALUATIONS

Safety data summaries will be displayed by randomization group for clinical safety laboratory test and ECG; adverse events and vital signs will be tabulated by treatment groups. Safety data listing by individual subject will be prepared for all safety endpoints.

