7.2. Adverse Events

Adverse events reported from Day 1 beginning at the Saline injection through the final follow-up will be considered treatment emergent adverse events (TEAEs). **Adverse event reported after Saline injection and prior to IC injection will be mapped to Saline treatment, all adverse events after IC injection, including events reported during the follow period will be mapped to IC treatment. For all AEs, if the onset date is missing/partial, the AE is TEAE and will be mapped to IC study unless the available portion of the date/time indicates otherwise.**

The Medical Dictionary for Regulatory Activities (Version 22) will be used to classify all AEs with respect to system organ class and preferred term.

The following summary tables will be produced for the TEAEs. All data summaries will provide number (%) subjects as well as total number of events in each category by treatment group (IC High, IC Low, and Overall).

1. a topline summary of TEAEs (**Table 14.3.2.1**)
2. a summary table by preferred term in descending order of total incidence (**Table 14.3.2.2**)
3. a summary table by system organ class and preferred term (**Table 14.3.2.3**)
4. a detailed summary table by system organ class, preferred term and severity (**Table 14.3.2.4.1**)
5. a detailed summary table by system organ class, preferred term and relationship (**Table 14.3.2.4.2**)
6. a table of serious TEAEs by system organ class and preferred term (**Table 14.3.2.5**)
7. TEAE leading to study discontinuation (**Table 14.3.2.6**)

In addition, adverse event of special interest (**Table 14.3.2.7**) will be identified and summarized if data warrant. Adverse event of special interest (AEOSI) could include but not limit to transient elevation of blood pressure and reflex bradycardia. For example, TEAE of tachycardia, hypotension, hypertension, rash or erythema, respiratory symptoms, such as dyspnea or

bronchospasm will be flagged as AEOSI. All adverse events will be reviewed before database lock to identify all AEOSI in the study.

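### The SAP gives two placement rules for mis-dosed subjects in the lab, ECG and PSAS displays, and its lab, ECG and adverse-event rules can attribute findings to IC in subjects who received only saline

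*SAP*

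**What the plan says.** SAP section 3.7 separates two kinds of group: "Hence, there are 2 randomization groups, namely IC High Dose and IC Low Dose and 3 treatment groups", the third treatment group being Saline. For a dosing error it says "the subject will be included in the actual treatment group received for efficacy, PK, and safety analyses". Section 3.3 repeats this for the two sets that matter here: "In the safety analysis set all subjects will be included in the actual treatment group received if a dosing error occurred", and "In the mITT analysis set all subjects will be included in the actual treatment group received if a dosing error occurred".

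The paragraph of 3.7 that follows the dosing-error rule says "Data presentation for study population, physician overall satisfaction, safety lab, and 12-ECG will be based on the 2 randomization groups". Section 7 agrees for two of these outputs: "Safety data summaries will be displayed by randomization group for clinical safety laboratory test and ECG". Section 7.5 again names the randomization group for ECG. Section 7.3 gives the lab columns as the two IC doses and an overall column, without saying how a subject is assigned to a dose. Section 5.2 tabulates PSAS by treatment.

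On subjects who stop after saline, section 3.3 admits to the Safety set anyone treated with either saline or IC. Section 4.1 foresees the subject who receives saline and "fails to receive a dose of IC, the subject will be considered to have discontinued study drug treatment". For adverse events, section 7.2 adds that "if the onset date is missing/partial, the AE is TEAE and will be mapped to IC study unless the available portion" of the date or time shows otherwise.

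**The concern.** Labs and ECG are safety analyses and PSAS is an efficacy analysis, so the as-treated rule and the randomization-group display rule both claim the same tables. If the display rule is taken literally, a subject randomized to High who was given Low has adverse events, vital signs and conspicuity scores under Low, but labs and ECG under High. Columns with the same label would then hold different subjects from table to table.

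The saline-only subject is a separate problem. This subject received no IC, yet the lab and ECG displays offer only an IC dose column or the overall column. Such a subject may have stopped because of an adverse event, so later abnormal findings are plausible, and they would be read as findings on IC.

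The safety profile of IC is the first secondary objective in section 2. Clinically important changes in laboratory tests and in ECG are named safety endpoints in section 2.1.2. PSAS is tested against a 50% limit within each dose and compared between doses, so placement can move its nominal p-values.

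**Working it through.** The plan states no figure on this point, so the check compares the text and then works out the scale.

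**Mis-dosed subjects**

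| Output | Text pointing to dose received | Text pointing to randomization group | Text that does not settle it |
|---|---|---|---|
| Labs | 3.3 (Safety set), 3.7 dosing-error rule | 3.7 display rule, section 7 | 7.3 (IC dose columns) |
| ECG | 3.3 (Safety set), 3.7 dosing-error rule | 3.7 display rule, section 7, 7.5 | none |
| PSAS | 3.3 (mITT set), 3.7 dosing-error rule, 5.2 (by treatment) | 3.7 display rule | none |

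Each output has at least one statement on each side, and no sentence says which prevails.

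**Saline-only subjects**

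1. They are in the Safety set (3.3), and section 4.1 expects that they may occur.
2. Section 2 gives all treated subjects a follow-up visit, and Table 1 schedules labs and ECG at that visit. They can therefore have post-treatment results.
3. The lab and ECG tables have columns for IC High, IC Low and overall only (7.3, 7.5). By randomization group, the subject falls in an IC column. By dose received, the subject fits only in the overall column. No rule addresses the case.
4. The as-treated rule is triggered by a dosing error, illustrated by a High/Low exchange. It does not clearly reach a subject who stopped after saline.
5. Section 7.2 assigns an undated adverse event to IC unless the known part of the date contradicts that. When the whole date is missing, nothing can contradict it, and there is no exception for a subject never given IC.
6. PSAS is analysed on the mITT set (section 5; Table 14.2.2 in section 8.1). That set requires both injections (3.3), so saline-only subjects cannot enter it.

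**Scale**

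Inputs: about 116 subjects (section 2). Allocation is taken as 1:1, as implied by 3.7, which expects the Saline group to be twice the size of each IC group. It is assumed that about all 116 are treated.

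- Subjects per dose in the Safety set: 116/2 = 58.
- Share of a dose column for k misplaced subjects: k/58. For k = 0 this is 0; k = 1, 1.7%; k = 2, 3.4%; k = 3, 5.2%.
- For PSAS, the 21 subjects treated before the score was developed are outside mITT, leaving (116 − 21)/2 = 47.5 per dose. One mis-dosed subject is 1/47.5 = 2.1% of a column.

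The values of k are illustrative, because the documents do not say how many such subjects there are.

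**The case against.** The strongest reply is that the two kinds of group in 3.7 differ only in whether Saline has its own column. Labs and ECG are scheduled at screening and follow-up, so they cannot be divided into a saline phase and an IC phase, and two columns are the natural layout. On that reading the display rule sets the number of columns, and the dosing-error rule still decides which column a mis-dosed subject enters. Other wording supports this. Section 3.7 describes a possible split of the Saline group by the IC dose that subjects received, 7.3 speaks of IC dose groups, and 5.4 cites 3.7 for two treatment groups in the TTV table, so the terms are used loosely. This stands to the extent that a reader may not infer a settled as-randomized rule for mis-dosed subjects. It does not remove the contradiction, because section 3.3 itself distinguishes the randomized group (ITT) from the group actually received (Safety, mITT, per protocol), and a programmer could reasonably take the display rule at its word.

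Three other stronger inferences also fail. Saline-only subjects do not contaminate PSAS. A mis-dosed subject did receive IC, only at the other dose, so absence of any IC exposure applies to saline-only subjects alone. The safety objective in section 2 concerns IC as a whole and is not worded by dose; the High versus Low comparison is exploratory.

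It is also fair to say that the stakes are limited. Lab and ECG tables carry no inferential statistics, and PSAS p-values are nominal. Dosing errors are to be documented in the study report, reasons for not receiving IC are tabulated, and drug administration, labs and ECG are listed by subject. The undated adverse event in a saline-only subject is an unlikely combination. These arguments bear on severity. They do not supply the missing rule.

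**Conclusion.** The point holds in two parts. For mis-dosed subjects, the SAP contains an unresolved contradiction over labs, ECG and, through the wording of 3.7 alone, PSAS. For saline-only subjects, following the stated display rule puts labs and ECG in an IC column without IC exposure, and following 7.2 attributes their wholly undated adverse events to IC. The benign reading of the two-group layout does not cure this second part, because it still gives these subjects no place except the overall column.

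Under 1:1 allocation and about 116 treated, each affected subject is about 1.7% of a dose column in the safety tables, and the effect is zero if no such subject occurs. The primary endpoint analysis is not touched. The matter should be corrected before the tables are programmed, but it does not threaten the trial's main conclusion.

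**What to change.** - In 3.7, 7, 7.3 and 7.5, state that the lab and ECG columns are by IC dose actually received.
- In 3.7, remove PSAS from the outputs shown by randomization group, and state in 3.7 and 5.2 that PSAS is shown by IC dose actually received.
- State where saline-only subjects appear in the lab and ECG tables, in a separate column or a footnote, and that they are outside the IC High and IC Low denominators.
- In 7.2, add that any adverse event in a subject who never received IC is mapped to Saline, however complete its date. The columns listed in 7.2 are IC High, IC Low and overall, whereas 3.7 promises three treatment groups for adverse events. The two should be aligned so that events mapped to Saline have a place.

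Demographics, medical history, protocol deviations and disposition may stay by randomization group.

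The cost is SAP wording and one column variable in programming. No new data are needed, since the doses given are already recorded.
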